13.3 Data Management

Data will be entered into the Oracle Clinical database and maintained at NYUSOM under the direction of staff in the BDM core.

THE ORACLE SYSTEM PROVIDES AUDIT trails that track creation and modification of records that includes userID and time stamp. Once entered, the data are subjected to validation procedures that are executed either immediately or upon saving the eCRF page or during the batch validation process. Validation failures that are identified before the page is saved can be corrected immediately. Validation failures during saving of the eCRF page and during batch validation processes will generate a discrepancy. Depending on the database account privileges, the data managers may be able to correct a discrepancy or if not, route it to the project data manager at NYU who can take appropriate action to correct the problem. Data clarification forms can also be printed out when necessary to be sent to the project data manager. Once the discrepancy is closed, by marking “resolved” or “irresolvable”, the data are marked clean and an audit trail is generated by the system.

All key end points will be source verified by a second person and errors will be corrected. Once the data are verified and all discrepancies are closed, the data can be locked/frozen. Locking and freezing can be done at different granular levels and will follow institutional SOPs and any specific requirements for the project.

Security measures that will be taken in order to protect patient data will include firewall technology and database level security which will be achieved by assigning roles and privileges to different levels of users and by requiring that the users authenticate themselves using userID and password. Additional security for data transfer between remote clients and servers will be achieved by using digital certificates/SSL. All data will be backed-up to tape periodically according to the Institutional SOPs. All data will be stored for at least 5 years following the termination of this study.

13.4 Confidentiality

The medical, hospital and research records associated with this study are considered confidential. Members of the treating team and designated study assistants will have access to the records as required to administer treatment and comply with the protocol. Neither the name nor any other identifying information for an individual will be used for reporting or publication regarding this study. All laboratory and baseline data will be de-identified and transferred via

secure links to the BDM core at NYU School of Medicine. Patient records will be made available for inspection to auditing agencies to satisfy regulatory requirements.

14 STATISTICAL CONSIDERATIONS

14.1 Endpoints/Objectives:

The primary objectives of this study are to:

1. To evaluate feasibility of prone IMRT to breast, level I- III (includes Cohort A) and supraclavicular nodes (physics and dosimetry parameters).
2. To estimate acute toxicity of prone IMRT to breast, level I- III (includes Cohort A) and supraclavicular nodes

Secondary objectives are to:

1. estimate the incidence of re-simulation to improve dosimetry after initial prone set-up
2. evaluate changes in QOL of patients assessed at baseline and after treatment
3. estimate incidence of late radiation toxicity (e.g., lymphedema, fibrosis and telangiectasia) and to examine genetic determinants of breast fibrosis

Exploratory objectives include:

Estimation of local recurrence rates; estimation of median disease-free survival; estimation of median time to progression, and estimation of median overall survival time.

14.2 Statistical Considerations, Sample Size and Interim Analysis Plans

14.3 Statistical Analysis

Descriptive statistics will be provided for all demographic and disease characteristics of patients at baseline using frequency distributions for qualitative variables and summary statistics (e.g., median, mean, etc.) and graphical displays (e.g., boxplots) for quantitative variables.

14.3.1 Primary Endpoints

The primary outcome of this study is the proportion of patients with acute toxicity greater than grade 2 (Skin toxicities grade 3 and above) occurring within 60 days after first day of treatment. This rate will be estimated with an exact 95% confidence interval. Treatment feasibility will be evaluated for each patient by the ability to meet all physics dose constraints as outlined in section 7.5.6. The proportion of patients who meet the constraints will be estimated with an exact 95% confidence interval.

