7.1 Treatment Planning using Hybrid IMRT Technique	26
7.2 Dose Specification	26
7.3 CT Simulation	26

7.4	Target Delineation	27
7.5	Technical Factors	27
7.6	Portal Imaging.....	29
8	DOSE MODIFICATIONS AND STOPPING CRITERIA.....	29
8.1	Dose Modification	29
8.2	Stopping Criteria.....	29
9	ADVERSE EVENTS: LIST AND REPORTING REQUIREMENTS	29
9.1	Adverse Events and Potential Risks List	29
9.2	Expedited Adverse Event Reporting	30
9.3	Routine Adverse Event Reporting Guidelines	30
10	CORRELATIVE/SPECIAL STUDIES	30
10.1	Blood Collection for TGF-beta 1 Polymorphism Determination	30
10.2	Lymphocyte Isolation, DNA Extraction, PCR Amplification and DNA Sequencing	30
10.3	Test Method	30
10.4	Denaturing High Performance Liquid Chromatography (DHPLC).....	32
10.5	Coding of Samples	32
11	INVESTIGATOR RESOURCES.....	32
11.1	Qualifications	32
11.2	Use of NYU Facilities.....	33
11.3	Conflict of Interest	33
12	STUDY CALENDAR	34
13	DATA REPORTING / REGULATORY CONSIDERATIONS.....	34
13.1	Monitoring Plan	34
13.2	Stopping Rules (for the individual patient and for the study as a whole)	35
13.3	Data Management	35
13.4	Confidentiality	35
14	STATISTICAL CONSIDERATIONS	36
14.1	Endpoints/Objectives:	36
14.2	Statistical Considerations, Sample Size and Interim Analysis Plans	36
14.3	Statistical Analysis.....	36
14.4	Accrual estimates	37
14.5	Sample Size Considerations/Interim Analysis.....	37
REFERENCES.....		39
APPENDIX 1 – COMMON TOXICITY CRITERIA		43
APPENDIX 2 – TOXICITY TRACKING FORM		45

APPENDIX 3 – QUALITY OF LIFE QUESTIONNAIRES 46
PROTOCOL SYNOPSIS

TITLE	Phase I - II Study of Prone Accelerated Breast and Nodal IMRT
STUDY PHASE	I - II
INDICATION	Stage II - III breast cancer (AJCC 2002)
PRIMARY OBJECTIVES	Feasibility, Acute toxicity
SECONDARY OBJECTIVES	Incidence of re-simulation supine, QOL (defined by RTOG-PRO), Late toxicity: e.g., fibrosis, telangiectasia, Local control: Time to Progression, Survival and evaluation of genetic determinants of breast fibrosis
EXPLORATORY OBJECTIVES	
HYPOTHESES	Prone IMRT to breast, level III and SCV nodes is feasible and well tolerated in a 3-week regimen
STUDY DESIGN	Prospective, single arm uncontrolled
PRIMARY ENDPOINTS	Acute, late effects, QOL-PRO
SAMPLE SIZE BY TREATMENT GROUP	104 patients. Cohort A – 30 patients
SUMMARY OF SUBJECT ELIGIBILITY CRITERIA	Newly diagnosed breast cancer patients after segmental mastectomy, and axillary dissection of at least 8 lymph nodes.
INVESTIGATIONAL PRODUCTS	
DOSAGE AND ADMINISTRATION	
CONTROL GROUP	N/A

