1. OBJECTIVES

- 1.1 Primary Objectives
 - 1.1.1 To evaluate feasibility of prone IMRT to breast, level III and supraclavicular nodes (physics and dosimetry parameters)
 - 1.1.2 To estimate acute toxicity of prone IMRT to breast, level III and supraclavicular nodes
- 1.2 Secondary Objectives
 - 1.2.1 To estimate the incidence of re-simulation to improve dosimetry after initial prone set-up
 - 1.2.2 To evaluate changes in QOL of patients assessed at baseline and after treatment
 - 1.2.3 To estimate incidence of late radiation toxicity (e.g., lymphedema, fibrosis and telangiectasia) and to examine genetic determinants of breast fibrosis
- 1.3 Exploratory Objectives
 - 1.3.1 To estimate local recurrence rates
 - 1.3.2 To estimate median Disease Free Survival (DFS)
 - 1.3.3 To estimate median Time to Progression
 - 1.3.4 To estimate median Overall Survival (OS)
- 1.4 Cohort A Objectives
 - 1.4.1 To explore feasibility of treating in the prone position a comprehensive nodal volume, that includes axillary nodal levels I and II in addition to the fields already treated per this protocol (i.e., axillary nodal levels III, supraclavicular fossa and breast or chest wall tangents, depending on whether the patient has undergone segmental mastectomy or mastectomy, respectively)

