7.3 CT Simulation

All patients will be CT scanned in the prone position on a specially designed board that allows the indexed breast tissue to fall freely below the board, granting unobstructed access to the breast through radiation ports from multiple beam angles. CT slice thickness should be 3.75 mm or less. Prior to the patient lying prone on the table for scanning, the borders of the breast/chest wall fields will be marked with radio-opaque CT fiducial markers. These markers will be used to outline the breast/chest wall treatment volume according to conventional treatment guidelines. Borders of the fields will be set medially at mid-sternum, laterally at the anterior edge of latissimus dorsi, superiorly at the bottom of the clavicular heads and inferiorly 2 cm from the infra-mammary fold. Patients will be tattooed with leveling marks for setup alignment with room lasers and for positioning the isocenter of the beams. A tattoo will be placed on the lateral breast tissue as a landmark for planning and positioning. Patients status post mastectomy will also be simulated prone with similar field borders. In addition, the chest wall scar will carefully be marked with radio-opaque CT fiducial markers.

Contouring of breast tumor bed, axillary level III nodes, supraclavicular nodes, indexed and contralateral breast tissue, ipsilateral brachial plexus, esophagus, heart, right and left lung, spinal cord, spinal cord plus 5 mm margin and right and left lobes of the thyroid will be

performed in order to guide beam arrangement and optimal normal tissue avoidance. In patients who have undergone pre-operative breast MRI, the breast glandular tissue will be contoured with the help of a radiologist co-investigator (Drs. [name] and [name]), to better inform the design of the treatment fields.

The patient will be CT scanned and treated in the supine position if the patient cannot lie prone, or if the prone plan fails to satisfy the dose constraints specified in Section 7.5.6

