7.5 Technical Factors

- 7.5.1 Dose calculations will include heterogeneity corrections.
- 7.5.2 Whole Breast fields – 3D tangents plus IMRT tangents
 1. The prone position requires careful placement of the isocenter during planning to avoid collision between the gantry and the breast board, couch, or patient.
 2. 3D tangents deliver nominally 67% of the whole breast dose, using 6 MV photons and including 2-3 cm flash. The fields are wedged and weighted to obtain a uniform dose distribution, normalized to allow approximately 105% maximum dose. 16 MV photons may be used for patients with large separations to reduce magnitude of dose maximum.
 3. IMRT tangents deliver nominally 33% of the whole breast dose, using 6 MV photons and including 2-3 cm flash. The 3D tangents are used as a base for optimization.

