7.5.6 Dose Constraints

The dose constraints below represent acceptance criteria for the resulting dose distribution.

1. Target volume dose constraints:
 - PTVTumor: $V \geq 98\%$
 - PTVBreast: $V \geq 95\%$
 - PTVNodesEval: $V \geq 95\%$
2. Normal tissue dose constraints:
 - a. Heart: $V < 5\%$
 - b. Ipsilateral lung: $V < 20\%$
 - c. Contralateral lung: $V < 15\%$
 - d. Spinal cord: 37.5 Gy maximum
 - e. Spinal cord plus 0.5 cm margin: 40 Gy maximum
 - f. Thyroid: contralateral lobe 15 Gy maximum
 - g. Esophagus: $V < 50\%$, 40.5 Gy maximum
 - h. Ipsilateral brachial plexus: 42 Gy maximum
 - i. Contralateral breast: Efforts should be made to keep the contralateral breast completely outside the primary beams

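### Could a passing supine plan count towards the feasibility of prone IMRT, because Section 14.3.1 does not name the plan that is scored?

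*Combined protocol and SAP*

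**What the plan says.** The first primary objective appears twice. Section 1.1.1 has "To evaluate feasibility of prone IMRT to breast, level III and supraclavicular nodes (physics and dosimetry parameters"), and Section 14.1 has "To evaluate feasibility of prone IMRT to breast, level I- III (includes Cohort A) and supraclavicular nodes (physics and dosimetry parameters"). Both say prone.

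Section 14.3.1 turns the objective into a measure: "Treatment feasibility will be evaluated for each patient by the ability to meet all physics dose constraints as outlined in section 7.5.6". The proportion meeting the constraints is to be reported with an exact 95% confidence interval. Section 14.5 adds a precision statement: with 104 patients, an observed proportion of at least 0.95 gives a lower limit of at least 0.89.

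Section 7.5.6 opens with "The dose constraints below represent acceptance criteria for the resulting dose distribution" and mentions no position. Section 7.3 has every patient scanned prone and then provides a fallback: "The patient will be CT scanned and treated in the supine position if the patient cannot lie prone, or if the prone plan fails" the limits in Section 7.5.6.

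The synopsis lists "Incidence of re-simulation supine" among the secondary objectives. Section 1.2.1 words the same item as "To estimate the incidence of re-simulation to improve dosimetry after initial prone set-up".

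**The concern.** Neither the endpoint sentence in 14.3.1 nor the section it points to says prone. Under 7.3, the patients who fail the prone test are the ones who receive a second, supine plan. If that plan is checked against 7.5.6 and passes, the patient has, on a literal reading, met all the constraints. The proportion would then show whether an acceptable plan existed in any position, which is a different question from whether prone IMRT is feasible. The error could only raise the estimate, and two analysts could report different values from the same data.

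There is also a denominator question. The eligibility criteria in 3.1 and 3.2 do not require a patient to be able to lie prone, 7.3 expects that some cannot, and nothing says whether they count as not feasible or drop out of the proportion.

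**Working it through.** **1. The plan's own figure.** Inputs from 14.5: n = 104, observed proportion at least 0.95, exact 95% interval (taken as two-sided). The smallest qualifying count is 0.95 × 104 = 98.8, rounded up to 99. The Clopper-Pearson lower limit is the 0.025 quantile of Beta(x, n − x + 1), and the upper limit is the 0.975 quantile of Beta(x + 1, n − x). For x = 99 this gives 99/104 = 0.952 with interval 0.891 to 0.984. The stated 0.89 is reproduced, but it does not show which plan is scored.

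**2. Which plan the text points to.**

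- 14.1 sets the objective as prone IMRT, judged on physics and dosimetry parameters. 14.3.1 then uses the physics dose constraints, so it is plainly the measure for that objective.
- 14.5 describes the same proportion as patients in whom this procedure is feasible. In a study of prone IMRT, the procedure is prone IMRT.
- 7.3 cites 7.5.6 only as the test of the prone plan. A patient who fails it is sent supine because prone did not work; scoring her as a prone success would contradict the objective.
- 7.5.2 is written with prone planning in mind: "The prone position requires careful placement of the isocenter during planning".

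The any-position reading works only if one sentence of 14.3.1 is cut off from 14.1, 14.5 and 7.3.

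**3. Size if supine passes were counted anyway.** Let k be the number of patients who pass only on a supine plan. With all 104 in the denominator, the overstatement is k/104, and 1/104 = 0.96 percentage points. The documents give no k, so the values below are assumptions. They start from 99 passes in any position, the smallest count that meets the 14.5 planning value:

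| k | Prone passes | Proportion | Exact 95% CI |
|---|---|---|---|
| 0 | 99/104 | 0.952 | 0.891 to 0.984 |
| 1 | 98/104 | 0.942 | 0.879 to 0.979 |
| 2 | 97/104 | 0.933 | 0.866 to 0.973 |
| 4 | 95/104 | 0.913 | 0.842 to 0.960 |

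A wider range can be borrowed from the earlier breast-only study in Section 2.3, where 5/200 right-sided (2.5%), 30/200 left-sided (15%) and so 35/400 overall (8.75%) were treated supine. Applied to 104 patients, these shares give 2.6, 15.6 and 9.1, or 3, 16 and 9 patients. If every final plan passed, any-position scoring would read 104/104 (lower limit 0.965) throughout. Prone-only scoring would read:

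- 3 supine: 101/104 = 0.971 (0.918 to 0.994)
- 9 supine: 95/104 = 0.913 (0.842 to 0.960)
- 16 supine: 88/104 = 0.846 (0.762 to 0.909)

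That study chose position by the volume of heart and lung in the field, not by 7.5.6, so this is a range and not a forecast.

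**4. The denominator.** Assume 97 pass prone, 5 fail prone and 2 cannot lie prone. Counting the 2 as not feasible gives 97/104 = 0.933 (0.866 to 0.973). Leaving them out gives 97/102 = 0.951 (0.889 to 0.984). The difference is 1.8 percentage points.

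**5. What depends on the proportion.** Section 14.5 sizes the trial on acute skin toxicity. Its interim boundaries concern skin toxicity, lymphedema and regional nodal recurrence. The feasibility proportion enters none of them, and 0.95 and 0.89 describe precision rather than a pass mark. Crossing them changes no decision.

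**The case for a change.** The best case for a change is that this is the only statistic planned for the first primary objective, that its prone meaning has to be inferred, that the possible error runs in the favourable direction only, and that a few sentences fixed before the results are known would remove it. Prone scoring would need no new data, since 7.3 already has the prone plan tested against 7.5.6.

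Part of this stands. The endpoint sentence does not say prone, and the handling of patients who cannot lie prone is unwritten. The secondary re-simulation figure would expose patients who failed prone and were replanned supine, but it may miss someone who was never simulated prone at all.

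The rest is weaker. The inference is short, because the prone objective sits in 14.1, inside the statistical section itself. The further worry about which prone plan counts after a repeat prone simulation has no described route: 7.3 and Section 2.3 give only a supine set-up after a failed prone plan, and the synopsis says supine, even though 1.2.1 omits the word. Reporting the proportion both with and without patients who cannot lie prone, without naming one as primary, would leave two estimates in place of one.

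**Conclusion.** No change to the plan follows. Section 14.3.1 leaves a definition unwritten that an analyst would fill in the same way from 14.1, 14.5 and 7.3: score the prone plan, and do not count a supine plan as a success. The large gaps in the working, up to 1.00 against 0.846, arise only under a reading that contradicts the stated objective and under supine shares borrowed from another study. Even then, the separately reported incidence of supine re-simulation would show a reader most of the difference.

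The remaining gap concerns patients who cannot lie prone. It is worth about one percentage point per patient, rests on a count the documents do not give, and affects no power, stopping or success rule. Stating the number of such patients and how they were counted, when the proportion is reported, deals with it.

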14.4 Accrual estimates

Estimated number of eligible patients for this trial is 4 - 6 patients per month. Since the recent publication of Giuliano AE (JAMA, 2011 Feb 9; 305(6):606-70), fewer axillary node dissection are being performed nationwide. Consequently, it is expected that the accrual to study NYU 09-0623 may slow down, because of fewer eligible patients. We expect to accrue 104 patients over 5 years.

Safety Stopping Rule; In addition, regional nodal recurrence will be monitored as the study progresses. If we enroll 104 patients over a three year period with follow-up of one year after the last patient is entered, the regimen will be considered ineffective if the null hypothesis that the proportion of regional nodal recurrences is 5% is rejected at an interim review.

Regional nodal recurrence is defined as recurrence within the axilla, level III or supraclavicular nodes, documented by PET-CT imaging and/or biopsy.

With 5 interim looks (every 21 patients who are followed for at least 1 year), with Pocock stopping boundaries, the trial would be stopped if the observed numbers of regional nodal recurrences are greater than or equal to 1 of the first 21 patients, and greater than 2, 4, 6, and 8 respectively at the second – fifth looks with an overall 1-sided alpha level of 0.05 and power of 0.62 [Calculations from EAST 5.2, Cytel, Inc., 2008].

REFERENCES

Archambeau, J. O., R. Pezner, et al. (1995). "Pathophysiology of irradiated skin and breast." *Int J Radiat Oncol Biol Phys* **31**(5): 1171-85.

Arnold, N., E. Gross, et al. (1999). "A highly sensitive, fast, and economical technique for mutation analysis in hereditary breast and ovarian cancers." *Hum Mutat* **14**(4): 333-9.

Atencio, D. P., C. M. Iannuzzi, et al. (2001). "Screening breast cancer patients for ATM mutations and polymorphisms by using denaturing high-performance liquid chromatography." *Environ Mol Mutagen* **38**(2-3): 200-8.

Baillet, F., M. Housset, et al. (1990). "The use of a specific hypofractionated radiation therapy regimen versus classical fractionation in the treatment of breast cancer: a randomized study of 230 patients." *Int J Radiat Oncol Biol Phys* **19**(5): 1131-3.

Bar Ad, V., A. Cheville, et al. (2009). "Time Course of Mild Arm Lymphedema After Breast Conservation Treatment for Early-Stage Breast Cancer." *Int J Radiat Oncol Biol Phys*.

Barendsen, G. W. (1982). "Dose fractionation, dose rate and iso-effect relationships for normal tissue responses." *Int J Radiat Oncol Biol Phys* **8**(11): 1981-97.

Bartelink, H., J. C. Horiot, et al. (2001). "Recurrence rates after treatment of breast cancer with standard radiotherapy with or without additional radiation." *N Engl J Med* **345**(19): 1378-87.

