8.2 Stopping Criteria

Regional nodal recurrences occur in 1 - 5% of patients with early stage breast cancer who have undergone mastectomy or breast conserving therapy (Fisher, Anderson et al. 2002; Moran and Haffty 2002; Harris, Hwang et al. 2003). While most nodal recurrences occur within the first five years after treatment, nodal recurrences have been documented for more than twenty years after completion of treatment (Lukens, Vapiwala et al. 2009).

Based on this data, a stopping rule for regional node recurrences will be implemented with an evaluation after every 21 patients are observed for at least 1 year post treatment. The schema is described in Section 14. This rule allows early stopping based on an excess of incidence of regional node recurrences (greater than 5% of patients).

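### The 5% nodal-recurrence null has no time point, so neither it nor the stated power of 0.62 is tied to the follow-up available at each look

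*Combined protocol and SAP*

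**What the plan says.** The safety stopping rule in section 14.5 calls the regimen ineffective if "the null hypothesis that the proportion of regional nodal recurrences is 5% is rejected at an interim review". The schedule is "With 5 interim looks (every 21 patients who are followed for at least 1 year), with Pocock stopping boundaries". The trial stops at one or more recurrences at the first look, then at more than 2, 4, 6 and 8 at looks two to five ("1 of the first 21 patients, and greater than 2, 4, 6, and 8 respectively at the second" and later looks). The stated properties are "overall 1-sided alpha level of 0.05 and power of 0.62". The alternative rate behind that power is not given.

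The rule assumes "If we enroll 104 patients over a three year period with follow-up of one year after the last patient is entered". Section 14.4 says "We expect to accrue 104 patients over 5 years". Section 5.3 limits follow-up visits to 5 years.

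The 5% comes from section 8.2: "Regional nodal recurrences occur in 1 - 5% of patients with early stage breast cancer who have undergone mastectomy or breast conserving therapy". The next sentence begins "While most nodal recurrences occur within the first five years after treatment" and adds that some have been seen more than twenty years later. The rule is then said to rest on these data. In the reference list, one of the three sources cited for the range is titled as a twenty-year follow-up of a randomised surgical trial. Section 13.2 repeats the 5% limit, again without a horizon.

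**The concern.** A cumulative recurrence proportion means little without the time by which it is reached. If 5% is what one expects over several years, patients followed for 1 to 4 years should show well under 5% even when the regimen only just meets the limit. Comparing their crude proportion with the full 5% then sets the bar too high. The bar also moves with accrual speed, because slower accrual gives the early patients more follow-up at each look.

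This matters most when the printed counts are repaired. They are far too strict for a flat 5%, and the natural correction is to recompute them to alpha 0.05 at 5%. That would replace a rule that stops too often with one that seldom stops. A trial that passed all five looks could then be read as having shown nodal control within the limit, when it had only been followed too briefly to show otherwise. This is the only numerical rule for nodal control in a study of a new technique with limited nodal fields in node-positive patients.

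**Working it through.** **Inputs.** From 14.5: null 5%; looks at 21, 42, 63, 84 and 104 patients; printed stopping counts ≥1, 3, 5, 7, 9; one-sided alpha 0.05; power 0.62; 3-year accrual. From 14.4: 5-year accrual. From 5.3: follow-up capped at 5 years. Assumed, because the documents do not say: the 5% and a doubled rate of 10% are cumulative rates at 5 years; accrual is uniform; there are no losses; every recurrence seen by a look is counted.

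**Step 1: the plan's own figures.** The stopping probability is the sum over looks of P(count reaches the boundary, with no earlier crossing), using binomial increments of 21, 21, 21, 21 and 20 patients.
- Printed counts at a flat 5%: 0.70. The first look alone gives 1 − 0.95^21 = 0.66. The stated alpha of 0.05 is not reproduced.
- Printed counts at a flat 10%: 0.96, not 0.62.
- Counts ≥5, 7, 8, 9, 10: alpha 0.045 at 5% and power 0.62 at 10%. The stated pair is therefore attainable, but only with different counts and only if the whole 10% has occurred by each look.

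**Step 2: what a regimen exactly at 5% by 5 years would show.** Constant hazard: λ = −ln(0.95)/5 = 0.01026 per year, or 1.03 per 100 patient-years. With 3-year accrual:
- Look 1: mean follow-up 1 + ½ × (20/104 × 3) = 1.29 years; 21 × 1.29 = 27 patient-years; expected 27 × 0.01026 = 0.28; crude proportion 0.28/21 = 1.3%.
- Look 5: mean follow-up 1 + ½ × (103/104 × 3) = 2.49 years; about 259 patient-years; expected 2.65; crude proportion about 2.5%.

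The regimen shows about a quarter to a half of the 5% against which it is tested.

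**Step 3: chance of stopping when the true rate is 10% by 5 years.** Simulation with counts ≥5, 7, 8, 9, 10. Both front-loaded patterns place 43% of the 5-year events in year 1. In the first, the rest fall evenly over years 2–5. In the second, the cumulative rate is proportional to (1 − e^(−0.5t))/(1 − e^(−2.5)).

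| Pattern | 3-year accrual | 5-year accrual |
|---|---|---|
| Constant hazard | 4% | 18% (20% without the 5-year cap) |
| Front-loaded, then even | 14% | 29% |
| Front-loaded, steadily declining | 26% | 39% |

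Another alpha-controlled set, ≥4, 6, 8, 9, 11 (alpha 0.0499, power 0.58 at a flat 10%), gives 2.5% and 12% with constant hazard. If the 10% is reached only by 10 years, that set stops in well under 1% of trials with constant hazard.

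**Step 4: the printed counts on the same time scale.** At 5% by 5 years with constant hazard they stop 25% (3-year accrual) or about 29% (5-year accrual) of the time. At 10% by 5 years they stop about 50% or 64% of the time.

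**Step 5: does one set of lower counts solve it?** Illustrative counts ≥3, 4, 5, 6, 7 stop a regimen exactly at 5% by 5 years 2.7% of the time with 3-year accrual and constant hazard, and stop the doubled rate 32% of the time. The false-stop rate rises to about 8% with 5-year accrual and constant hazard, to 8% and 15% under the first front-loaded pattern, and to about 14% and 20% under the second. No set of counts can be judged until horizon and accrual are fixed.

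**The case against.** The strongest reply is that the horizon is an inference. Section 8.2 puts no time on its 1–5% range, and the remark about the first five years carries a different citation. A reader might infer that the 5% is a 5-year rate; the documents do not say so. This stands, and 5 years is used above only as an assumption. It does not remove the defect, because a null with no time point cannot be matched to any follow-up.

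A reader might also infer that the trial as written would seldom stop for poor nodal control. It would not be so: the printed counts stop too often. The insensitivity belongs to a rule whose counts have been corrected and whose time scale has not. Nor is it correct that a doubled rate would almost never be caught, since the answer runs from 4% to 39% with the assumed recurrence pattern and accrual.

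Three further inferences go too far. The rule is not the only safeguard: section 13 has the monitoring committee review safety at least yearly, with power to recommend modification or termination. The plan does not say that a patient who recurs and leaves before 1 year is dropped; the 1-year requirement may serve only to time the looks, so this is an ambiguity. And a longer accrual does not stretch protocol follow-up beyond 5 years.

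Finally, few events and short follow-up limit any rule here. Even the lower illustrative counts miss the doubled rate 68% of the time with 3-year accrual and constant hazard. Matching the null to time recovers part of the lost power, not all of it.

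**Conclusion.** The point holds in this form: the plan tests a 5% null with no time point on patients followed from 1 year, gives two accrual periods, and states a power that none of these inputs supports. Correcting the counts alone would leave a rule that usually misses a doubled rate. The size is a stopping probability of about 4–20% with constant hazard and about 15–30% with front-loaded recurrence (up to 39% under the steeper pattern), against the stated 0.62. These figures assume 10% by 5 years, uniform accrual over 3 or 5 years, no losses, all recurrences counted, and boundaries of ≥5, 7, 8, 9, 10. The direction is the same in every scenario run; the exact size depends on a horizon and hazard shape that the documents do not supply. The excess stopping from the printed counts is a separate error and needs its own correction.

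**What to change.** In sections 8.2, 13.2 and 14.5, state the time by which the 5% applies and the alternative rate for which power is claimed. Use one accrual period in 14.4 and 14.5. Recompute boundaries and power on that time scale in one of two ways:

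- compare observed recurrences in all treated patients with the number expected from accumulated patient-years (for example 1.03 per 100 patient-years if the 5% is a 5-year rate with constant hazard); or
- use a fixed window, such as 1 year, with a null for the same window.

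State that a recurrence counts whenever it occurs, whatever the later follow-up. Report false-stop probability and power under at least one constant and one front-loaded pattern. Derive the counts for the chosen horizon and accrual; ≥3, 4, 5, 6, 7 is an illustration and keeps false stops under 5% only with 3-year accrual and constant hazard. The final limit and counts are for the sponsor's statistician and the monitoring committee.

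The cost is rewording, a recalculation and, for the first option, a patient-year tally at each look. The stated power is likely to be less favourable than 0.62. No new data are needed.
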